# 8.4.2. Toxicity Considerations

Toxicities associated or possibly associated with Atezolizumab treatment should be managed according to standard medical practice. Additional tests, such as autoimmune serology or biopsies, may be used to determine a possible immunogenic etiology. Although most immunerelated adverse events (irAEs) observed with immunomodulatory agents have been mild and self-limiting, such events should be recognized early and treated promptly to avoid potential major complications. Discontinuation of Atezolizumab may not have an immediate therapeutic effect and, in severe cases, immune-related toxicities may require acute management with topical corticosteroids, systemic corticosteroids, mycophenolate, or TNF $\alpha$  inhibitors.

The primary approach to Grade 1 to 2 irAEs is supportive and symptomatic care with continued treatment with Atezolizumab; for higher-grade irAEs, Atezolizumab should be withheld and oral and/or parenteral steroids administered. Recurrent Grade 2 irAEs may also mandate withholding Atezolizumab or the use of steroids. Assessment of the benefit-risk balance should be made by the investigator, with consideration of the totality of information as it pertains to the nature of the toxicity and the degree of clinical benefit a given patient may be experiencing prior to further administration of Atezolizumab. Atezolizumab should be permanently discontinued in patients with life-threatening irAEs.

#### 8.4.2.1. Infusion-related reactions (IRRs)

The management of infusion-related reactions (IRRs) will be according to severity as follows:

	In the event that a patient experiences a mild (NCI CTCAE Grade 1) IRR, the infusion rate
	should be reduced to half the rate being given at the time of event onset. Once the event
	has resolved, the investigator should wait for 30 minutes while delivering the infusion at the
	reduced rate. If tolerated, the infusion rate may then be increased to the original rate.
_	In the count that a matient commitment and another IDD (NOLOTOAT Orests O) and the biggs

In the event that a patient experiences a moderate IRR (NCI CTCAE Grade 2) or flushing, fever, or throat pain, the infusion should be immediately interrupted and the patient should receive aggressive symptomatic treatment. The infusion should be restarted only after the

symptoms have adequately resolved to baseline grade. The infusion rate at restart should be half of the infusion rate that was in progress at the time of the onset of the IRR.

For severe or life-threatening IRRs (NCI CTCAE Grade 3 or 4), the infusion should be stopped immediately, and aggressive resuscitation and supportive measures should be initiated. Patients experiencing severe or life-threatening IRRs will not receive further infusion and will be further managed as clinically indicated until the event resolves.

#### 8.4.2.2. **Gastrointestinal Toxicity**

Immune-mediated colitis has been associated with the administration of Atezolizumab. Patients should be advised to inform the investigator if any diarrhea occurs, even if it is mild.

If the event is of significant duration or magnitude, or is associated with signs of systemic inflammation or acute phase reactants (e.g., increased CRP or platelet count or bandemia), it is recommended that sigmoidoscopy (or colonoscopy, if appropriate) with colonic biopsy with three to five specimens for standard paraffin block be performed. If possible, one or two biopsy specimens should be snap frozen and stored.

Treatment may be restarted following the resolution of colitis. In addition, if the patient is being managed with corticosteroids, treatment should not be restarted until the steroids have been tapered down to a prednisone dose ≤ 10 mg/day. Patients who resume treatment should be monitored closely for signs of renewed diarrhea.

#### 8.4.2.3. Hepatotoxicity

Immune-mediated hepatitis has been associated with the administration of Atezolizumab. While in this study, patients presenting with right upper-quadrant abdominal pain felt by the investigator to be possibly related to study treatment and/or unexplained nausea or vomiting should have LFTs performed immediately, and LFTs (AST/ALT) should be reviewed before administration of the next dose of study drug.

In the presence of LFT abnormalities, neoplastic, concurrent medications, viral hepatitis, and toxic etiologies should be considered and addressed, as appropriate. Imaging of the liver, gall bladder, and biliary tree should be performed to rule out neoplastic or other causes of increased LFTs. Anti-nuclear antibody, perinuclear anti-neutrophil cytoplasmic antibody, anti-liver kidney microsomal, and anti-smooth muscle antibody tests should be performed if an autoimmune etiology is suspected.

#### 8.4.2.4. Dermatologic Toxicity

Treatment-emergent rash has been associated with Atezolizumab. The majority of cases of rash were mild in severity and self-limited, with or without pruritus.

A dermatologist should evaluate persistent and/or severe rash or pruritus. A biopsy should be performed unless contraindicated. Low-grade rash and pruritus irAEs have been treated with symptomatic therapy (e.g., antihistamines). Topical or parenteral corticosteroids may be required for more severe symptoms.

#### 8.4.2.5. **Endocrine Toxicity**

Hypothyroidism has been associated with the administration of Atezolizumab. Patients with unexplained symptoms such as fatigue, myalgias, impotence, mental status changes, or constipation should be investigated for the presence of thyroid, pituitary, or adrenal endocrinopathies, as well as for hyponatremia or hyperkalemia.

An endocrinologist should be consulted if an endocrinopathy is suspected. Thyroid-stimulating hormone (TSH) and free T4 levels should be obtained to determine whether thyroid abnormalities are present. TSH, prolactin, and a morning cortisol level will help to differentiate primary adrenal insufficiency from primary pituitary insufficiency.

#### 8.4.2.6. **Pulmonary Toxicity**

Dyspnea, cough, fatigue, hypoxia, pneumonitis, and pulmonary infiltrates have been associated with the administration of Atezolizumab and have primarily been observed in patients with underlying NSCLC.

Mild-to-moderate events of pneumonitis have been reported with Atezolizumab. All pulmonary events should be thoroughly evaluated for other commonly reported etiologies such as pneumonia/infection, lymphangitic carcinomatosis, pulmonary embolism, heart failure, chronic obstructive pulmonary disease (COPD), or pulmonary hypertension and the following should be performed:

	Measurement of oxygen saturation (i.e., arterial blood gas) High-resolution CT scan of the chest Bronchoscopy with bronchoalveolar lavage and biopsy Pulmonary function tests (with diffusion capacity of the lung for carbon monoxide [DLco])				
	Patients will be assessed for pulmonary signs and symptoms throughout the study. Patients will also have CT scans of the chest at every tumor assessment.				

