Grade 4							
Pulmonary (Cob	imetinib or Atezolizumab)						
	Mild-to-moderate events of pneumonitis have been reported with atezolizumab and						
Comoral	cobimetinib. All pulmonary events should be thoroughly evaluated for other commonly						
General guidance	reported etiologies such as pneumonia/infection, lymphangitic carcinomatosis, pulmonary embolism, heart failure, chronic obstructive pulmonary disease, or pulmonary hypertension.						
guidance	For events concerning for pneumonitis, consider comprehensive infectious evaluation						
	including viral etiologies.						
D	Continue atezolizumab and cobimetinib.						
Pneumonitis,	Re-evaluate on serial imaging.						
grade 1 (asymptomatic)	Consider patient referral to pulmonary specialist.						
(asymptomatic)	For recurrent pneumonitis, treat as Grade 3 or 4 event.						
	Withhold atezolizumab and cobimetinib.						
	Refer patient to pulmonary and infectious disease specialists and consider bronchoscopy						
	or BAL.						
D :::	• If bronchoscopy is consistent with immune-related etiology, initiate treatment with 1–2						
Pneumonitis,	
 
mg/kg/day oral prednisone or equivalent.
 
Resume atezolizumab and cobimetinib if event resolves to Grade 1 or better within 12
 
						
grade 2	Resume alezolizumab and codimetinib ii event resolves to Grade 1 or better within 12 weeks.						
	
 
Permanently discontinue atezolizumab and cobimetinib and contact Medical Monitor if
 
						
	event does not resolve to Grade 1 or better within 12 weeks.						
	For recurrent events, treat as a Grade 3 or 4 event.						
	Permanently discontinue atezolizumab and cobimetinib.c						
	Refer patient to pulmonary and infectious disease specialists and consider bronchoscopy						
	or BAL.						
Pneumonitis,	
 
If bronchoscopy is consistent with immune-related etiology, initiate treatment with 1−2
 
						
grade 3/4	mg/kg/day oral prednisone or equivalent.						
	If pulmonary event does not improve within 48 hr or worsens, consider adding an						
	immunosuppressive agent (e.g., infliximab, cyclophosphamide, IV lg, or mycophenolate						
	mofetil).  • If event resolves to Grade 1 or better, taper corticosteroids over ≥ 1 month.						
	The event resolves to Grade 1 of Detter, taper conticosteroids over 2 1111011th.						

Hepatic (Cobimetinib	or Atezolizumab)

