Amylase or lipase elevation, Grade 3 or 4	
 
Withhold Atezolizumab.
 
Resume Atezolizumab if event resolves to Grade 1 or better within 12 weeks
 
Permanently discontinue Atezolizumab if event does not resolve to Grade 1 or better within 12 weeks
 
For recurrent events, permanently discontinue Atezolizumab
 
				
Immune-related pancreatitis, Grade 2 or 3	
 
Withhold Atezolizumab
 
Resume Atezolizumab if event resolves to Grade 1 or better within 12 weeks
 
Permanently discontinue Atezolizumab if event does not resolve to Grade 1 or better within 12 weeks
 
For recurrent events, permanently discontinue Atezolizumab
 
				
Immune-related pancreatitis, Grade 4	Permanently discontinue Atezolizumab.				
Skin and subcutaned	ous (Cobimetinib or Atezolizumab)				
General guidance	A dermatologist should evaluate persistent and/or severe rash or pruritus. A biopsy should be considered unless contraindicated.				

 
Continue atezolizumab and cobimetinib.
 
Initiate supportive care (e.g., antihistamines, topical corticosteroids). If event do not improve, consider treatment with higher-potency topical corticosteroids.
 
For grade 2 rash, consider referral to dermatologist.
 
Acneiform rash:
 
Consider topical corticosteroids (e.g., hydrocortisone 2.5%, alclometasone) an antibiotics (minocycline, doxycycline, or antibiotics covering skin flora) as clinic indicated.
 
					

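### For pneumonitis, Section 8.4.2.6 and the Section 8.5 pulmonary table give conflicting instructions on bronchoscopy at every grade, and no text says which governs

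*Combined protocol and SAP*

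**What the plan says.** Section 8.4.2.6 (Pulmonary Toxicity) sets its scope broadly: "All pulmonary events should be thoroughly evaluated for other commonly reported etiologies such as pneumonia/infection". After naming further alternative causes it continues "chronic obstructive pulmonary disease (COPD), or pulmonary hypertension and the following should be performed". The list that follows has four items: oxygen saturation, high-resolution chest CT, "Bronchoscopy with bronchoalveolar lavage and biopsy", and pulmonary function tests with diffusion capacity. No item carries a grade threshold or a condition.

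The pulmonary table in Section 8.5, headed for cobimetinib or atezolizumab, repeats the instruction to evaluate all pulmonary events thoroughly but omits the procedure list. Its general-guidance row adds "For events concerning for pneumonitis, consider comprehensive infectious evaluation". The graded rows, which are for pneumonitis only, then say:

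- Grade 1: continue both drugs, "Re-evaluate on serial imaging", and consider referral to a pulmonary specialist. Recurrent pneumonitis is handled as Grade 3 or 4.
- Grade 2 and Grade 3/4, in the same words: "Refer patient to pulmonary and infectious disease specialists and consider bronchoscopy", with lavage named as the alternative. Steroids follow if the bronchoscopy points to an immune-related cause.

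On skin, Section 8.4.2.4 says of persistent and/or severe rash or pruritus: "A biopsy should be performed unless contraindicated". The general-guidance row of the Section 8.5 skin table says "A biopsy should be considered unless contraindicated". The Grade 3 row of that table says that a biopsy should be done where appropriate.

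**The concern.** The two pulmonary texts are both operative safety instructions for the same drug and the same event, and they differ on an invasive procedure. A site that works from 8.4.2.6 has an instruction to carry out bronchoscopy with lavage and biopsy even for an asymptomatic Grade 1 finding. A site that works from the 8.5 table has no such instruction at Grade 1 and a discretionary one, without biopsy, above that.

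Two things are at stake. The first is patient burden: participants with the same event may or may not be sent for an invasive test, depending on which page the site opens. The second is consistency of management. From Grade 2 upward the table makes steroid treatment conditional on a bronchoscopy result, so a difference in work-up can become a difference in treatment. The trial is multicenter and the adverse event profile is a Phase II secondary endpoint, so one rule applied everywhere is worth having.

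**Working it through.** No arithmetic applies. The check is a side-by-side reading of the two sections, followed by a search for text that would settle which one governs.

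**Step 1: pneumonitis, row by row.**

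| Grade | Section 8.4.2.6 | Section 8.5 pulmonary table | Agree? |
|---|---|---|---|
| 1 | Bronchoscopy with lavage and biopsy *should* be done | Serial imaging; *consider* referral; bronchoscopy not mentioned | No |
| 2 | Same | Referral; *consider* bronchoscopy or lavage; biopsy not mentioned | No |
| 3/4 | Same | Same wording as Grade 2 | No |

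The texts differ in three ways: whether bronchoscopy is called for at all (Grade 1), how strongly (Grade 2 and Grade 3/4), and whether it includes biopsy (never mentioned in the table).

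**Step 2: link to steroids.** In the Grade 2 and Grade 3/4 rows, starting steroids depends on bronchoscopy supporting an immune-related cause. The line before makes bronchoscopy something to consider. Those rows do not say what happens to the steroid decision if it is not done. A site following 8.4.2.6 would have the result; a site following only the table might not.

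**Step 3: pulmonary events other than pneumonitis.** The table has no graded row for them. Its general-guidance row asks for thorough evaluation and names no procedures. Here the table is silent rather than contradictory, and the 8.4.2.6 list stands without a grade limit.

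**Step 4: skin biopsy.** There are three wordings: to be performed unless contraindicated (8.4.2.4, persistent and/or severe events), to be considered unless contraindicated (8.5, general guidance), and to be performed if appropriate (8.5, Grade 3). The first two cover the same persistent and/or severe events and differ in strength. At Grade 3 the table moves most of the way back towards 8.4.2.4, so this inconsistency is smaller than the pulmonary one.

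**Step 5: is there a governing clause?** The introduction to Section 8.4.2 says that tests such as biopsies may be used to look for an immune cause. This is general and does not withdraw the specific pulmonary list that follows it. Section 8.6 deals with approval of departures from the dose-modification guidelines, not with which diagnostic text prevails. Neither section refers to the other on this point.

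**The case against.** The best defence is that 8.4.2.6 should not be read in isolation. Its parent section directs management according to standard medical practice and treats biopsy as optional, the verb is *should*, and the protocol uses *must* elsewhere for steps it means to be mandatory. A sensible investigator would not biopsy the lung for a trivial finding. That is a fair account of likely practice. It does not give sites a single rule, and it does not explain why the same protocol drops bronchoscopy altogether for Grade 1 pneumonitis in 8.5.

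The defence also limits the point, because four stronger readings are tempting and the documents do not support them.

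- *Any cough sets the two sections in conflict.* The graded rows cover pneumonitis only. For cough or dyspnea the table gives no contrary instruction on procedures, so there is a gap but no contradiction.
- *Resumption of atezolizumab depends on which section is followed.* In the pneumonitis rows, Grade 1 continues, Grade 2 resumes on resolution to Grade 1 or better within 12 weeks, and Grade 3/4 stops permanently. None of this depends on bronchoscopy. The only link is indirect: Section 8.5 requires steroids, once started for an atezolizumab-related toxicity, to be tapered before resumption.
- *A number of affected patients can be estimated.* The documents give no rate of pneumonitis in this population, and 8.4.2.6 itself says that the pulmonary events were seen mainly in patients with lung cancer.
- *Causality attribution requires bronchoscopy.* The attribution rules in Sections 15.3.2 and 15.3.3 rest on investigator judgment and name no procedure.

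The steroid consequence also has a limit. The introduction to 8.4.2 separately provides for steroids in higher-grade immune-related events, so an event already judged immune-related at Grade 3/4 has another route to them.

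**Conclusion.** The contradiction is real and confined to pneumonitis. Sections 8.4.2.6 and 8.5 disagree on bronchoscopy in all three graded rows, and no text resolves it. From Grade 2 upward, the table's steroid trigger relies on a test that the table leaves optional. The skin biopsy wordings are a lesser inconsistency of the same kind.

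This is an inconsistency in safety guidance. It does not touch the sample size, the two-stage decision rule or the analysis of 16-week progression-free survival. That sites would in fact differ in practice is an inference from the wording; the documents do not state it. The conclusion that the passages must be reconciled does not depend on that inference, or on any assumed event rate. Nothing here implies that either instruction is the clinically right one.

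**What to change.** Reconcile Section 8.4.2.6 with the Section 8.5 pulmonary table, and Section 8.4.2.4 with both the general-guidance and Grade 3 rows of the Section 8.5 skin table. State once, in one place, which events and grades call for which procedures, including whether biopsy is part of bronchoscopy. Make the other section refer to that text. The same text should say whether the procedure list applies to pulmonary events other than pneumonitis, and how the steroid step is to be read when bronchoscopy has not been done. The clinical leads decide the rule; this review proposes none.

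The cost is a wording amendment to three sections. It needs no additional patients and no change to the statistical section.

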	8.4.2.7. Systemic Immune Activation				
es who diff ike	stemic immune activation (SIA) is a rare condition characterized by an excessive immune sponse. Given the mechanism of action of Atezolizumab, SIA is considered a potential risk en given in combination with other immunomodulating agents. SIA should be included in the ferential diagnosis for patients who, in the absence of an alternative etiology, develop a sepsise syndrome after administration of Atezolizumab, and the initial evaluation should include the owing:				
	CBC with peripheral smear PT, PTT, fibrinogen, and D-dimer Ferritin Triglycerides AST, ALT, and total bilirubin LDH Complete neurologic and abdominal examination (assess for hepatosplenomegaly)				
f S	SIA is still suspected after the initial evaluation, contact the Medical Monitor for additional				

#### 8.4.2.8. Pancreatic Toxicity

Symptoms of abdominal pain associated with elevations of amylase and lipase, suggestive of pancreatitis, have been associated with administration of other immunomodulatory agents. The differential diagnosis of acute abdominal pain should include pancreatitis. Appropriate workup should include an evaluation for obstruction, as well as serum amylase and lipase tests.

recommendations.

#### 8.4.2.9. Potential Eye Toxicity

An ophthalmologist should evaluate visual complaints. Uveitis or episcleritis may be treated with topical corticosteroid eye drops. Atezolizumab should be permanently discontinued for immunemediated ocular disease that is unresponsive to local immunosuppressive therapy.

## 8.4.2.10. Immune-mediated Nephritis

Immune-related nephritis has been associated with the administration of atezolizumab. Eligible patients must have adequate renal function, and renal function, including serum creatinine, should be monitored throughout study treatment. Patients with abnormal renal function should be evaluated and treated for other more common etiologies (including prerenal and postrenal causes, and concomitant medications such as nonsteroidal anti-inflammatory drugs). Refer the patient to a renal specialist if clinically indicated. A renal biopsy may be required to enable a definitive diagnosis and appropriate treatment. If no alternative cause of acute kidney injury is identified, patients with signs and symptoms of acute kidney injury, in the absence of an identified alternate etiology, should be treated according to the management guidelines for immune-related renal events in the table below.

Event	Management
Grade 1 Renal Event	
 
Continue atezolizumab.
 
Monitor kidney function, including creatinine, closely until values resolve to within normal limits or to baseline values.
 

Grade 2 Renal Event	
 
Withhold atezolizumab for up to 12 weeks after event onset. a
 
Refer patient to renal specialist.
 
Initiate treatment with corticosteroids equivalent to 1- 2 mg/kg/day oral prednisone.
 
If event resolves to Grade 1 or better, resume atezolizumab.b
 
If event does not resolve to Grade 1 or better while withholding atezolizumab, permanently discontinue atezolizumab and contact Study Chair.c
 

Grade 3 or 4 Renal Event	
 
Permanently discontinue atezolizumab and contact Study Chair.
 
Refer patient to renal specialist and consider renal biopsy.
 
Initiate treatment with corticosteroids equivalent to 1- 2 mg/kg/day oral prednisone.
 
If event does not improve within 48 hours after initiating corticosteroids, consider adding an immunosuppressive agent.
 
If event resolves to Grade 1 or better, taper corticosteroids over ≥ 1 month.
 

Note: Management guidelines are presented by adverse event severity based on NCI CTCAE and are applicable to both CTCAE Version 4.0 and CTCAE Version 5.0.

<sup>a Atezolizumab may be withheld for a longer period of time (i.e., > 12 weeks after event onset) to allow for corticosteroids (if initiated) to be reduced to the equivalent of ≤ 10 mg/day oral prednisone. The acceptable length of the extended period of time must be agreed upon by the investigator and the Study Chair.

b If corticosteroids have been initiated, they must be tapered over ≥ 1 month to the equivalent of ≤ 10 mg/day oral prednisone before atezolizumab can be resumed.

eResumption of atezolizumab may be considered in patients who are deriving benefit and have fully recovered from the immunerelated event. Patients can be re-challenged with atezolizumab only after approval has been documented by both the investigator (or an appropriate delegate) and the Study Chair.

## 8.4.2.11. Immune-related Myositis

Myositis or inflammatory myopathies are a group of disorders sharing the common feature of inflammatory muscle injury; dermatomyositis and polymyositis are amongst the most common disorders. Initial diagnosis is based on clinical (muscle weakness, muscle pain, skin rash in dermatomyositis). biochemical (serum creatinine-kinase increase). and (electromyography/MRI) features, and is confirmed with a muscle-biopsy. One etiology of myositis is immune-mediated, which is the current concern with atezolizumab.

It is recommended that atezolizumab should be withheld for moderate or severe (Grade 2 or 3) immune-related myositis and permanently discontinued for recurrent severe or life-threatening myositis (recurrent Grade 3 and Grade 4). Please refer the patient to rheumatologist and/or neurologist and consider muscle biopsy and supportive measures as clinically indicated. Corticosteroids treatment with 1-2 mg/kg/day IV methylprednisolone or higher-dose bolus if severely compromised (weakness severely limiting mobility, cardiac function, respiratory function, dysphagia) and/or additional immunosuppressive agents should be administered for ≥ Grade 2 events or if the event does not improve after initial corticosteroids. Please refer to the table below for detailed management guidelines for immune-mediated myositis.

Management Guidelines for Immune-Related Myositis:

Event	Management
Immune-related Myositis	Continue atezolizumab
Grade 1	

Refer patient to a rheumatologist or neurologist

Initiate treatment per institutional guidelines

Immune-related Myositis Grade 2	
 
Initiate treatment per institutional guidelines
 
Withhold atezolizumab for up to 12 weeks after event onset and contact the Study Chair
 
Refer patient to a rheumatologist or neurologist
 
Initiate treatment per institutional guidelines
 
Consider treatment with corticosteroid equivalent to 1-2 mg/kg/day IV methylprednisolone and convert to 1-2 mg/kg/day oral prednisone or equivalent upon improvement
 
If corticosteroids are initiated and event does not improve within 48 hours after initiating corticosteroids, consider adding an immunosuppressive agent.
 
If event resolves to Grade 1 or better, resume atezolizumab
 
If event does not improve to Grade 1 or better while withholding atezolizumab, permanently discontinue atezolizumab and contact the Study Chair.
 

Event	Management
Immune-related Myositis	☐ Withhold atezolizumab for up to 12 weeks after event onset
Grade 3	and contact the Study Chair
	☐ Refer patient to a rheumatologist or neurologist
	☐ Initiate treatment per institutional guidelines
	□ Respiratory support may be required in more severe cases.
	☐ Initiate treatment with corticosteroids equivalent to 1-2
	mg/kg/day IV methylprednisolone or higher-dose bolus if
	patient is severely compromised (e.g. cardiac or respiratory symptoms, dysphagia, or weakness that severely limits
	mobility); convert to 1-2 mg/kg/day oral prednisolone or
	equivalent upon improvement
	☐ If event does not improve within 48 hours after initating
	coritosteroids, consider adding an immunosuppressive
	agent
	☐ If event resolves to Grade 1 or better, resume atezolizumab
	☐ If event does not improve to Grade 1 or better while
	withholding atezolizumab, permanently discontinue
	atezolizumab and contact the Study Chair.
1 1 1 1 1 1 1 1 1 1 1 1 1 1 1 1 1 1 1 1	For recurrent events, treat as a Grade 4 event
Immune-related Myositis Grade 4	☐ Permanently discontinue atezolizumab and contact the
Grade 4	Study Chair  Refer patient to rheumatologist or neurologist.
	☐ Initiate treatment as per institutional guidelines. Respiratory
	support may be required in more severe cases.
	☐ Initiate treatment with corticosteroids equivalent to 1-2
	mg/kg/day IV methylprednisolone or higher-dose bolus if
	patient is severely compromised (e.g. cardiac or respiratory
	symptoms, dysphagia, or weakness that severely limiting
	mobility); convert to 1-2 mg/kg/day oral prednisone or
	equivalent upon improvement.
	☐ If event does not improve within 48 hours after initiating
	corticosteroids, consider adding an immunosuppressive agent.
	
 
If event resolves to Grade 1 or better, taper corticosteroids
 

	over ≥ 1 month.
	Over = 1 monun.

safety and efficacy as specified in the protocol.

